	analyze the relationship between the quantitative variables: change in pH and change in Cardiac Contractility, assuming an alpha risk of 5% (95% confidence level), a 20% beta risk (power of 80%) and a minimum ratio that has an estimated clinical significance with a correlation coefficient of 1.5, a bilateral estimate of sample size of 346 subjects is obtained. Assuming a 5% loss (17 individuals) during the study a total of 363 cases would be necessary.
Trial design and methods	It is not a trial
Trial duration per participant:	It is not a trial
Main inclusion/exclusion criteria:	
EXCLUSION CRITERIA
 
 • Atrial or ventricular arrhythmia: you need a stable pulse to measure the contour. • Aortic, mitral or tricuspid valve insufficiency. In the case of valve insufficiency the valve does not close correctly. Therefore, the thermodilution curve is affected by indicator regurgitation, resulting in a prolonged indicator decay time. • Intra-Aortic Balloon pump: once again, the pulse contour is all wrong; but you can still get thermodilution cardiac output measurements. • Aortic aneurysm: the contour will be bizarre because the arterial compliance is going to be weird, with the aortic aneurysm acting as a damping system by absorbing all the pressure wave. • Extracorporeal circuit: when you are on bypass, there is no real arterial waveform • Pneumonectomy: PiCCO relies on there being a relatively normal pulmonary vasculature. • Massive pulmonary embolism: as above; it is essentially a pneumonectomy by embolism. • Intracardiac shunt: the PA catheter will also give an inaccurate thermodilution reading. • Less than a minimal tidal volume 6-

Full title of the research: **The impact of systemic pH on cardiac function and clinical outcome in the critically ill patient.**

IRAS Project ID: **227870**

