4 STUDY DESIGN

- Study population and groups: those patients on haemodynamic monitoring in ICU (PiCCO monitoring)
- **Calculation of the sample size:**

Taking into account that the primary objective of the study is to analyze the relationship between the quantitative variables: change in pH and change in Cardiac Contractility, assuming an alpha risk of 5% (95% confidence level), a 20% beta risk (power of 80%) and a minimum ratio that has an estimated clinical significance with a correlation coefficient of 1.5, a bilateral estimate of sample size of 346 subjects is obtained. Assuming a 5% loss (17 individuals) during the study a total of 363 cases would be necessary.

- **Statistical methods:**

The description of quantitative variables is carried out with central tendency and dispersion indices, whether based on values (mean and standard deviation) or on ordinations (median and interquartile range) according to whether they meet normality or not, respectively. Its graphic representation is done with Histograms and Cash Diagrams. The description of categorical variables is performed with absolute and relative frequencies in percentages. Its graphic representation is done with bar charts.

Full title of the research: **The impact of systemic pH on cardiac function and clinical outcome in the critically ill patient.**

IRAS Project ID: **227870**

The relationship between categorical variables is analyzed by comparing proportions with the Pearson Chi-square test, provided that there are less than 20% of squares in the contingency table with expected frequencies less than 5. In the case that there is more 20% of squares with expected frequencies less than 5, the Fisher's exact test is used bilaterally.

The magnitude of the effect of the relationship between two binary variables has been analyzed with the Ratios of proportions or Relative Risk and with the Odds Ratio.

The relationship between a binary exposure variable and a quantitative response is analyzed with the Student-Fisher t test for independent samples if the normality condition is met. According to whether or not the equality of variances are met, the Student-Fisher t test is used for independent groups for homogeneous variances or for non-homogeneous variances, respectively. In case of not fulfilling the condition of normality, the comparison of two means is made with the non-parametric Mann-Whitney U test.

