The comparison between a polytomic predictor and a quantitative response is made through the analysis of variance (ANOVA) in the case of meeting the conditions of normality and homogeneity of variances. If any of these conditions is not met, it is done with the non-parametric H test of Kruskal-Wallis. If the polytomic predictor is ordinal, the ANOVA trend test or the non-parametric Jonckheere-Terpstra trend test is also used, depending on whether normality is met or not, respectively.

Full title of the research: **The impact of systemic pH on cardiac function and clinical outcome in the critically ill patient.**

IRAS Project ID: **227870**

The relationship between two independent quantitative variables is evaluated with the correlation coefficient r of Pearson if normality is met, or with the nonparametric correlation coefficient ρ of Spearman if normality is not met. Its graphic representation is made with the scatter diagrams or points.

Normality is assessed with the Kolmogorov-Smirnov test with the Lilliefors significance correction for large samples, or with the Shapiro-Wilks test for small samples. The equality of variances is analyzed with the Levene variance homogeneity test.

The relationship between two related quantitative variables is performed using the Student-Fisher t-test for related samples in case the normality condition is met. Otherwise, the non-parametric Wilcoxon T test is used. The relationship between two paired categorical variables is performed by the McNemar symmetry test.

The relationship between a continuous quantitative response and one or several predictors, whether binary, polytomic or quantitative, is done with Simple or Multiple Linear Regression respectively.

The polytomous predictors variables are introduced in the Linear Regression models broken down into binary indicator variables coded with respect to the first reference category.

An estimative multivariate linear regression model of the effect of the predictor Change of pH (between the lowest and highest pH) on the response Change in cardiac output

Full title of the research: **The impact of systemic pH on cardiac function and clinical outcome in the critically ill patient.**

IRAS Project ID: **227870**

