5 STUDY SCHEDULE

Approximately:

- April 2018: Start collecting data from patient already in the ICU with the inclusion criteria.
- April 2018- September 18 approximately until reach the minimum number of 360 patients
- October-November 18 data analysis

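### The sample size rests on a correlation coefficient of 1.5, which cannot exist; 346 fits 0.15, so this is very likely a decimal slip to confirm and correct

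*Combined protocol and SAP*

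**What the plan says.** Section 4, under Calculation of the sample size, sizes the study on the relationship between change in pH and change in cardiac contractility. It gives these inputs and results:

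- Type I error: "assuming an alpha risk of 5% (95% confidence level".
- Type II error: "a 20% beta risk (power of 80" percent.
- Effect size and result: "estimated clinical significance with a correlation coefficient of 1.5, a bilateral estimate of sample size of 346 subjects is obtained".
- After a 5% allowance for loss, counted as 17 individuals: "a total of 363 cases would be necessary".

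The Target sample size row of the Study summary repeats the same effect size and result: "a correlation coefficient of 1.5, a bilateral estimate of sample size of 346 subjects is obtained".

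Under Statistical methods in section 4, the association between two quantitative variables is "evaluated with the correlation coefficient r of Pearson if normality is met, or with the nonparametric correlation coefficient" of Spearman otherwise. Section 8 says the same.

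Section 5 (Study schedule) has data collected "until reach the minimum number of 360 patients".

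**The concern.** Pearson's r and Spearman's rho both lie between -1 and 1. A smallest relevant correlation of 1.5 is therefore not an ambitious or doubtful assumption but an impossible one, and no sample size follows from it.

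The effect size is the input that tells a reader what the study is built to detect. As printed, the reader cannot learn that value, cannot reproduce 346, and cannot judge whether the target is sensible without working the formula backwards. The misprint also hides how small the likely target is. That matters when a small significant correlation, or a null result, comes to be interpreted. If the original calculation used something other than 0.15, the sample size itself could be wrong.

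**Working it through.** **Inputs.** From section 4: alpha 0.05, two-sided (the plan says bilateral); power 0.80; r = 1.5 as printed; n = 346 before loss; 5% loss, taken as 17; total 363. From section 5: minimum 360.

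**Formula.** For one correlation, by the Fisher z transformation:

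n = ((z for 1 - alpha/2 + z for power) / atanh(r))^2 + 3, with 1.960 + 0.842 = 2.802.

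**Step 1: the plan's own inputs.** atanh(1.5) is undefined, so there is no n. The stated 346 cannot be reproduced.

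**Step 2: r = 0.15.** atanh(0.15) = 0.1511. Then (2.8016 / 0.15114)^2 + 3 = 343.6 + 3 = 346.6, which matches 346 to within rounding. The bias-corrected version gives 345.6. Solving back from n = 346 gives r = 0.1501.

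**Step 3: how specific is the match?**

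| r (two-sided 5%, 80% power) | n |
|---|---|
| 0.10 | 782.7 |
| 0.14 | 398.2 |
| 0.149 | 351.3 |
| 0.15 | 346.6 |
| 0.151 | 342.0 |
| 0.16 | 304.4 |
| 0.20 | 194.0 |

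At r = 0.15, a one-sided test would need 273.6 and 90% power would need 463.0. The stated two-sided test at 80% power is the combination that fits.

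**Step 4: could 1.5 be some other measure?**

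- As a Fisher z value (r = 0.905), it needs about 7 subjects.
- As a hazard ratio, it needs 191 events (Schoenfeld) or 197 (Freedman).
- As an odds ratio, it needs 776 to 1,822 subjects for assumed control rates of 10% to 50%.
- As a risk ratio, it comes near 346 only at an assumed control rate between 25% (430) and 30% (326). The documents give no such rate, and they describe both variables as quantitative.

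**Step 5: size of the likely target.** 0.15^2 = 0.0225, so change in pH would explain about 2.3% of the variance.

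**Step 6: loss and the schedule.** 0.05 x 346 = 17.3, taken as 17, and 346 + 17 = 363, so the allowance is consistent on the plan's own terms. From 360, a loss of 17 leaves 343, and a 5% loss leaves 360 x 0.95 = 342. Power at r = 0.15 is the normal probability below atanh(0.15) x sqrt(n - 3) - 1.960:

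- n = 346: 0.15114 x 18.520 - 1.960 = 0.839, power 79.9%.
- n = 343: 0.15114 x 18.439 - 1.960 = 0.827, power 79.6%.
- n = 342: 0.15114 x 18.412 - 1.960 = 0.823, power 79.5%.

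The largest difference is 79.9 - 79.5 = 0.4 percentage points.

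**The case against.** The strongest reply is that this is a misprint in one sentence that happens to appear twice. The fit to 0.15 is tight, and once the value is corrected no patient count and no test changes. That is fair, and it limits the severity. It does not remove the point, because a reader reaches 0.15 only by inverting the formula, and only the investigators can say what was actually entered.

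Four narrower objections have some force:

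- **360 against 363.** The schedule is headed as approximate, and a minimum of 360 does not forbid 363. The power difference is also smaller than the spread between formulas: at n = 343 the Fisher z, bias-corrected Fisher z and noncentral t methods give 79.6%, 79.7% and 80.0%. This is a consistency point and no more.
- **Variance explained.** The 2.3% figure applies to Pearson's r. If the analysis switches to Spearman, the squared coefficient describes ranks, not the variance of the outcome.
- **Justification of the threshold.** Asking why 0.15 is the smallest relevant correlation goes beyond the arithmetic and depends on that value being confirmed. It is reasonable to ask, because neither sample size passage gives a reason, but it is secondary.
- **Scope of the reassurance.** Only the simple correlation calculation was checked. The estimative regression in section 4 models change in cardiac output with adjustment for confounders, whereas the sample size refers to change in contractility. Confirming 0.15 says nothing about the power of that model.

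**Conclusion.** The concern holds. A correlation of 1.5 is impossible for the coefficients the plan names, and 346 cannot follow from the printed inputs. That part is certain and needs no assumption beyond the range of a correlation.

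That 0.15 was intended is very likely but remains an inference. It rests on the plan's own alpha, sidedness and power, a standard formula, and the absence of any competing reading supported by the documents. If it is right, the simple correlation calculation is sound, 346 and 363 stand, and the fault is one of reporting. The error should be fixed because it affects a key design value, but it is not evidence that the study is too small. The 360 against 363 mismatch is minor, at about half a percentage point of power or less.

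**What to change.** 1. Check the original sample size calculation for the correlation that was entered.
2. If it was 0.15, replace 1.5 with 0.15 in section 4 (Calculation of the sample size) and in the Target sample size row of the Study summary. Leave 346 and 363 as they are. State that this is an R-squared of about 2.3% on the Pearson scale, and add one sentence on why it is the smallest correlation of clinical interest.
3. If another value was used, state it and restate either the sample size or the power to match.
4. In section 5, use 363; or keep 360 and note that power at r = 0.15 is then about 79.5% to 79.6% by the Fisher z formula.

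If 0.15 is confirmed, the cost is one number in two places, one or two added sentences, one number in the schedule, and at most 363 - 360 = 3 more records. If another value was used, the sample size or power has to be recalculated.

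### The recruitment minimum of 360 in Section 5 does not leave the 346 evaluable patients for which Section 4 requires 363

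*Combined protocol and SAP*

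**What the plan says.** The sample-size paragraph appears twice with the same content, in the Study Summary (target sample size row) and in Section 4 (Study Design, calculation of the sample size). It sets a 5% alpha and 80% power, takes "a minimum ratio that has an estimated clinical significance with a correlation coefficient of 1.5", and concludes that "a bilateral estimate of sample size of 346 subjects is obtained". It then allows for loss: "Assuming a 5% loss (17 individuals) during the study a total of 363 cases would be necessary".

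Section 5 (Study Schedule) gives the recruitment period as April to September 2018, "approximately until reach the minimum number of 360 patients". The documents do not explain why this figure is 360 rather than 363.

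**The concern.** The sample size is the study's only stated recruitment target, and it carries two values. A figure described as necessary is followed by a minimum that is three lower. A site working from Section 5 could consider recruitment complete before the Section 4 requirement is met, and a reader of the final report could not tell whether 360 patients fulfilled the plan.

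A second ambiguity lies in the allowance for loss. The 17 losses are calculated on the 346 evaluable patients, whereas loss during a study occurs among those enrolled. The plan does not say what the 5% is a percentage of, and the answer decides whether 363 is enough.

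**Working it through.** **Inputs.** From Section 4: two-sided alpha 0.05, power 80%, evaluable N = 346, loss 5% given as 17 individuals, total 363. From Section 5: minimum 360.

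**Reproducing 363.** 346 × 0.05 = 17.3, taken as 17, and 346 + 17 = 363. Equivalently, 346 × 1.05 = 363.3. The plan's figure is reproduced as N × (1 + d), where d is the loss rate.

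**Evaluable patients under each reading of the loss.**

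| Enrolled | 17 patients lost | 5% of enrolled lost |
|---|---|---|
| 363 | 363 − 17 = 346 | 363 × 0.95 = 344.85 |
| 360 | 360 − 17 = 343 | 360 × 0.95 = 342 |

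At 363 the plan is met exactly on the first reading and missed by about one patient on the second. At 360 it is missed by three or four patients. For 360 to leave 346, losses could not exceed 14 patients, and 14/360 = 3.9%, below the plan's own 5%.

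**Total consistent with 5% of those enrolled.** N/(1 − d) = 346/0.95 = 364.2, rounded up to 365. Check: 365 × 0.95 = 346.75, whereas 364 × 0.95 = 345.8 falls just short.

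**Effect on power.** This step needs an assumption. A correlation cannot be 1.5, and the Fisher z formula is undefined at that value. Reading it as 0.15 gives

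n = ((1.960 + 0.842)/atanh(0.15))² + 3 = 346.6,

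which is close to the stated 346. A variant with the small-sample bias correction reaches 80% at exactly 346. A one-sided calculation at 0.15 gives 274 and does not match.

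Under that assumption, power = Φ(atanh(0.15) × √(n − 3) − 1.960):

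- n = 346: 79.9%
- n = 344.85: 79.8%
- n = 342: 79.5%

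With the bias correction, power is 80.0% at 346 and 79.6% at 342. On either version the loss is under half a percentage point.

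**The case against.** The strongest defence concerns 363. The plan states the loss as a count as well as a percentage, and 363 − 17 = 346 exactly. Dividing by (1 − d) is the better convention, but the plan's addition is coherent on its own terms. That 17/363 is 4.7% rather than 5% carries no weight, since 4.7% rounds to 5% and the loss rate is unsourced. This defence stands: a reader might infer that 363 is an arithmetic error, and the documents do not support that without the further premise that the 5% applies to those enrolled.

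The defence of 360 is weaker. Section 5 is a calendar headed as approximate, and 360 may be a rounded planning number. A minimum also does not forbid recruiting further. So a reader who inferred that the plan has two competing stopping rules would be going too far: 363 is described as necessary, not as a stopping point, and the two statements of the sample size agree with each other. What remains is that a number labelled a minimum has been rounded below the requirement, and no reading of the plan's own loss allowance brings it back to 346.

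It can also be said that the point is tiny beside the impossible coefficient in the same sentence. That is true of its size. The coefficient is a separate matter, however, and correcting it to 0.15 would leave the difference between 363 and 360 in place.

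**Conclusion.** The point holds as a minor inconsistency. The Section 5 minimum of 360 does not deliver the stated 346 evaluable patients: it leaves 342 or 343, three or four short, whichever way the loss is read. This needs no assumption beyond the plan's own loss allowance.

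For 363 the conclusion is conditional. It is sufficient if 17 patients are lost, and about one patient short if 5% of enrolled patients are lost, in which case 365 is the consistent total.

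A reader might infer that the study is materially underpowered because of this. It is not. The change from 346 to 342 costs less than half a percentage point of power, and even that estimate rests on reading 1.5 as 0.15. On the uncorrected formula 346 itself gives 79.9%, so a power just under 80% cannot be attributed to the loss allowance alone.

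**What to change.** Give one enrolment figure in the Study Summary, Section 4 and Section 5, and state what the 5% is a percentage of. Any of these is consistent:

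- **365**, with the loss defined as 5% of those enrolled;
- **363**, with the loss defined as 17 patients, and Section 5 raised to 363;
- **360**, with the evaluable number restated as about 342.

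The cost is wording in at most three places. Recruitment rises by at most two patients above the stated 363 (five above 360), or not at all under the third option.

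Correct the printed coefficient first. If the base number changes, the enrolment total must be recalculated from it. Rounding up the uncorrected formula, for example, gives 347, and 347/0.95 = 365.3, or 366. No restated power should enter the protocol until the coefficient is settled.

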5 STUDY SCHEDULE

Approximately:

- April 2018: Start collecting data from patient already in the ICU with the inclusion criteria.
- April 2018- September 18 approximately until reach the minimum number of 360 patients
- October-November 18 data analysis

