Full title of the research: **The impact of systemic pH on cardiac function and clinical outcome in the critically ill patient.**

IRAS Project ID: **227870**

	
remain in the model if they are significant and are removed from the model if they are not significant.
 
In the multivariate models of linear regression, the criterion of clinical significance has been used to decide on the maintenance or withdrawal of the predictors in each step. They remain in the model if they produce a change greater than 10% in the coefficient of the predictor of interest (presence of confounding bias) and withdraw if the change is less than 10% (absence of confounding bias).
 
The conditions of application of the simple or multiple linear regression (linearity, independence, normality and equality of variances) are evaluated by analysing the residuals.
 
Values of $P < 0.05$ are considered significant. The statistical treatment has been performed the statistical package SPSS, version 18 (SPSS Inc, Chicago, IL, USA).

STUDY TIMELINES	
Study Duration/length	Approximately 6 months
Expected Start Date	April 2018
End of Study definition and	Expected on November 2018

Full title of the research: **The impact of systemic pH on cardiac function and clinical outcome in the critically ill patient.**

IRAS Project ID: **227870**

anticipated date	
Key Study milestones	March study submission April 2018 start of data collection October –November data analysis
STORAGE of SAMPLES (if applicable)	No applicable
Human tissue samples	No applicable
Data collected / Storage	Observational data will be completely anonymous before digital storage and sending for analysis. Previous to that, it will be collected on paper form which will be encrypted coded.

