1 INTRODUCTION

Why?

We would like to perform an analysis of the relationship between systemic pH and cardiac function and clinical outcome in critically ill patients in patients hospitalized the Intensive Care Unit.

How is it of relevance and importance to patients and public?

Studying this subject we could provide important information about the impact of systemic pH on cardiac function and clinical outcome in seriously ill patients and enable the clinician to

Full title of the research: **The impact of systemic pH on cardiac function and clinical outcome in the critically ill patient.**

IRAS Project ID: **227870**

understand the best treatment of these patients. Patients will be studied who had cardiac monitoring during their ICU admission and an acid-base metabolic disorder. We exclude those patients with cardiac history or who presented an acute coronary syndrome during ICU admission.

IT IS NOT A THERAPEUTIC STUDY. ONLY OBSERVATIONAL. NO INTERVENTIONS.

Where?

In seven different ICU's between King's College NHS Foundation Hospital and Lewisham and Greenwich NHS Trust

How?

The study will take approximately six month to collect prospectively data from each unit. The data will be extracted from the medical notes and ICU charts. No active involvement with participants.

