2 BACKGROUND AND RATIONALE

3 OBJECTIVES

Goals

Primary

1. Assess whether there are significant changes in cardiac function associated with changes in blood pH.
2. Relate the changes in cardiac function to presence or absence of underlying cardiac disease.

Secondary

3. To establish which factors affected by blood pH have an impact on cardiac function.

Full title of the research: **The impact of systemic pH on cardiac function and clinical outcome in the critically ill patient.**

IRAS Project ID: **227870**

4. Study the mortality of patients admitted to the Intensive Care Unit (ICU) who had continuous cardiac monitoring at any time during their admission and relate it to changes in blood pH.

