12 MATERIAL/SAMPLE STORAGE

There is usually a copy of this in the site file and on our network drive. This is only accessible by appropriate hospital staff and outside researchers only if patient consents. Therefore research team knows who the number relates to and could trace back if necessary but no-one else. This is why we refer to an enrolment log in the IRAS form because we need some way of linking patients to data.

- If samples will be stored for future use (and the details): data will be store for about six months. There is usually a copy of this in the site file and on our network drive.
- Measures for the processing, control and safe storage of samples: no tissue samples.
- Details of data controller/custodian. It will be Chief investigator , myself ([name])

NOT APPLICABLE :In the study, will be collected from patients in accordance with the patient consent form and patient information sheet and shall include all tissue samples or other biological materials and any derivatives, portions, progeny or improvements as well as all patient information and documentation supplied in relation to them. Samples will be processed, stored and disposed in

Full title of the research: **The impact of systemic pH on cardiac function and clinical outcome in the critically ill patient.**

IRAS Project ID: **227870**

accordance with all applicable legal and regulatory requirements, including the Human Tissue Act 2004 and any amendments thereafter.

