20 ARCHIVING

Date of birth	
Sex (M/F)	
Hospital ADMISSION date	
ICU ADMISSION date	

 • Unplanned/emergency admission. • Planned /elective admission. 	
ICU DISCHARGE date	
Discharged alive from ICU?	(Y / N)

 • From ICU to home directly. • From ICU to hospital ward. • From ICU to another ICU (other hospital) 	
Discharged alive from HOSPITAL?	(Y / N)

 • Home • Nursing home or equivalent 	
28-day mortality. Death occurring within 28 days of hospital discharge?	(Y / N)
Admitting diagnosis group:	

 • Cardiac arrest/ other causes of cardiogenic shock • Cardiothoracic surgery • Septic shock 
 ➢ Medical ➢ Neutropenic sepsis/ other haematology & oncology sepsis ➢ Surgical • Post-operative management: any other speciality 	

 • Haemorrhagic shock 
 ➢ Major trauma ➢ Gastrointestinal/other medical ➢ Post-surgical • Acute respiratory failure 
 ➢ COPD /asthma exacerbation ➢ Pneumonia ➢ Other causes • Acute renal failure requiring hemofiltration • Trauma/neuro-surgical • Decompensated liver disease/ acute liver failure • Diabetic ketoacidosis/hyperosmotic syndrome • Others 	

PATIENT RESEARCH ENCRYPTED CODE:
	

Chronic diseases
 
 • Ischaemic heart disease. • Congestive heart failure • Atrial fibrillation/Atrial flutter • Devices 
 ➢ Pacemaker (PM) +/- Implantable cardioverter-defibrillator (ICD) ➢ Cardiac resynchronization therapy (CRT) +/- (ICD) • Arterial hypertension • Pulmonary hypertension • Pulmonary embolus/deep vein thrombosis • COPD/Asthma • Fibrosis • Diabetes mellitus • End stage kidney disease (on regular dialysis) • Chronic kidney disease or pre-dialysis (NOT on dialysis) • Liver disease • Morbid obesity. • Recent quimiotherapy / radiotherapy (last 30 days) • Haematology malignancies 
 ➢ Acute myeloid leukaemia (AML) ➢ Chronic lymphocytic leukaemia (CLL) ➢ Myeloma ➢ Lymphoma • Other hemato-onco malignancies 	

Severity scores
 
 • APACHE II 	

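### No outcome follow-up is scheduled between last enrolment and analysis, so hospital and post-discharge deaths may be incomplete and the secondary mortality analysis (goal 4) may be biased

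*Combined protocol and SAP*

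**What the plan says.** Section 5 (Study schedule), which is marked as approximate, plans data collection "April 2018- September 18 approximately until reach the minimum number of 360 patients", followed by "October-November 18 data analysis". The study timelines in the summary give the end of study as "Expected on November 2018". Neither place sets an outcome cut-off or a follow-up period after the last patient enters.

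Secondary goal 4 (section 3), which sets mortality against pH change, is to "Study the mortality of patients admitted to the Intensive Care Unit (ICU) who had continuous cardiac monitoring at any time during their admission". It names no time point.

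The data collection form, printed under section 20 (Archiving), has three survival items, all yes/no: "Discharged alive from ICU", the same question for the hospital, and "Death occurring within 28 days of hospital discharge". It lists home, a nursing home and an ICU in another hospital among the discharge destinations.

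On sources, section 1 says: "The data will be extracted from the medical notes and ICU charts. No active involvement with participants". Section 11 describes an enrolment log holding name, hospital number and study ID, and section 12 says the team could trace a patient through it. No use of the log to establish vital status is planned. The statistical methods (sections 4 and 8) contain no time-to-event method and no rule for patients whose stay is unfinished.

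**The concern.** Two of the three survival items cannot be answered at enrolment plus a fixed number of days. Hospital survival waits for the end of the stay, and the post-discharge item needs 28 further days. A schedule that moves from enrolment to analysis leaves these open for patients enrolled late or staying long.

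The second gap is one of source, not time. A death at home, in a nursing home or in another hospital need not appear in the notes of the enrolling hospital. That affects every patient discharged or transferred, and waiting longer does not cure it.

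Patients with unresolved status are not a random part of the cohort, since length of stay and transfer are likely to be related to severity and to acid-base course. If they are dropped or misclassified, the relation between pH change and mortality can be distorted. Clinical outcome is in the study title, although mortality is only a secondary goal.

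**Working it through.** The plan gives no figure for outcome completeness, so there is none to reproduce. The check is calendar arithmetic plus a simple model.

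**From the documents:** enrolment April to September 2018, taken as 1 April to 30 September (183 days); minimum 360 patients; analysis October to November; post-discharge window 28 days.

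**Assumed, because the documents are silent:** even enrolment; log-normal stay from enrolment to the end of the hospital stay, median m = 20 days (range 14 to 30), log SD 0.8; hospital mortality d = 20% to 40%, with the same stay distribution for deaths and survivors; outcomes cut at 1 October, 31 October or 30 November.

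**Calendar.** The three cuts fall 1, 31 and 61 days after 30 September. A patient enrolled on 30 September who stays 20 days reaches the end of the post-discharge window on 17 November (20 + 28 = 48 days). For that window to close by 30 November the stay must be at most 61 − 28 = 33 days; by 31 October, at most 31 − 28 = 3 days.

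**Model.** For time t from enrolment to the cut, the probability of still being in hospital is S(t) = 1 − Φ((ln t − ln m)/0.8).

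- H, the share still in hospital, is the average of S(t) over the 183 enrolment days.
- P is the average of S(t − 28), with S = 1 when t is 28 days or less. It is the share whose stay plus 28 days is unfinished.
- P overstates the missing post-discharge status, because a patient who died in hospital needs none. The share lacking that status is U = H + (1 − d)(P − H).

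Results for m = 20:

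| Cut | H | P | U, d = 40% | U, d = 20% | U in 360 patients |
|---|---|---|---|---|---|
| 1 October | 14.7% | 29.9% | 14.7 + 0.6 × 15.2 = 23.8% | 14.7 + 0.8 × 15.2 = 26.9% | 86–97 |
| 31 October | 4.1% | 13.6% | 4.1 + 0.6 × 9.5 = 9.8% | 4.1 + 0.8 × 9.5 = 11.7% | 35–42 |
| 30 November | 1.4% | 3.8% | 1.4 + 0.6 × 2.4 = 2.8% | 1.4 + 0.8 × 2.4 = 3.3% | 10–12 |

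**Sensitivity to the median, same log SD.**

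- 1 October, lowest (m = 14): 10.2 + 0.6 × (25.5 − 10.2) = 19.4%. Highest (m = 30): 21.9 + 0.8 × (36.9 − 21.9) = 33.9%.
- 30 November, lowest: 0.5 + 0.6 × (1.6 − 0.5) = 1.2%. Highest: 4.1 + 0.8 × (8.7 − 4.1) = 7.8%.

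**Sensitivity to the shape of the stay.** With fixed or exponential stays of 10 to 45 days, the share still in hospital is 5–24% at 1 October, 0–12% at 31 October and 0–6% at 30 November.

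**Effect on a mortality proportion.** With a share u unknown and mortality p among the known, the all-alive and all-dead bounds are (1 − u)p and (1 − u)p + u. For an assumed p = 20%: u = 10% gives 18% to 28%; u = 25% gives 15% to 40%.

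The model covers timing only. It does not estimate deaths missed after discharge or transfer, for which the documents give no basis.

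**The case against.** A reader might infer that hospital survival cannot be complete and that goal 4 mortality will be wrong. The documents do not support that. The dates are approximate, no data lock on 1 October is stated, and analysis runs through November. A late-November cut leaves about 1% still in hospital under the central assumptions. Medical notes, not only ICU charts, are a source and can show hospital discharge status. Goal 4 is secondary with no time point, and ICU death could serve it with little harm from the schedule. This objection stands against the stronger wording. It does not remove the point, because the plan chooses neither a late cut nor ICU death.

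A reader might also infer that patients still admitted would be entered as deaths, or that deaths elsewhere would be entered as survivals. No text says so, and the form as shown may be partial: it ends at the severity score and shows no pH or PiCCO fields. The missing options are a gap, not evidence of miscoding.

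Nor does the statement in section 12 that "data will be store for about six months" show that records would be lost before analysis. It answers a template prompt about stored samples and gives no starting point.

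Finally, the stay lengths, the log SD and the hospital mortality are all assumed, and no bias in the pH–mortality relation itself has been estimated.

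**Conclusion.** The point holds as a risk of incomplete and possibly biased mortality data, not as a certain error. As written, the plan has no outcome follow-up period, no closing date, no rule for unfinished stays and no stated source for deaths after discharge or transfer.

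Under even enrolment, log-normal stays (median 20 days, log SD 0.8) and 20–40% hospital mortality, about 24–27% of patients lack post-discharge status at 1 October, 10–12% at 31 October and 3% at 30 November. With medians of 14 to 30 days the range is about 19–34% at the first cut and 1–8% at the last. The size thus depends mainly on a cut-off the plan does not state. Under-recording of deaths outside hospital comes on top and cannot be sized from the documents. Only secondary goal 4 is affected.

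**What to change.** - State in section 3 that the goal 4 outcome is death in hospital, reported together with death in ICU.
- Add to section 5 an outcome closing date a fixed period after the last enrolment, and start the goal 4 analysis only then. If that runs past November, move the end date for that analysis.
- Add two categories to the form: still in hospital at closure, and transferred with status unknown. Report how many patients fall in each, and give a sensitivity analysis counting them all as dead and then all as alive. Do not simply treat them as censored: that censoring would be informative, and the plan has no time-to-event method.
- Use the 28-day post-discharge item only if vital status is obtained through the hospital number on the enrolment log. Otherwise leave it out of the goal 4 analysis.

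The cost is a short delay to the goal 4 analysis, two form categories and one sensitivity analysis, plus the tracing work if the post-discharge item is kept. Goals 1 to 3 keep their dates.
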